The aim of this study is to test whether and to what degree a community-based karate class tailored for individuals with early- to middle-stage Parkinson's Disease (PD) 1) is feasible; and 2) improves objective and patient-reported outcomes. The benefits of exercise for general health and wellbeing in older adults are well-established. Balance exercises such as tai chi and yoga, along with resistance training, can improve or maintain physical function in older adults and enhance muscle strength. Furthermore, aerobic activity is critical for maintaining and improving cardiovascular and functional health. Non-contact boxing has recently seen a surge in popularity among individuals with PD, with components of both aerobic and balance exercise. While participants anecdotally note improvements in stress and physical function, this has only been minimally studied. However, drawing on this experience and the combined aerobic, balance, and mindfulness practices that comprise karate, we hypothesize that participation in structured karate programs may offer similar or greater benefits. In particular, the aerobic, resistance, and balance aspects of karate may be beneficial for physical and cognitive wellbeing, and the mindfulness exercise may improve overall wellbeing. Therefore, we propose a pilot, 10 week-long study of a structured karate exercise program for people with early to middle PD, with pre- and post-intervention assessment of mobility, gait, balance, falls, attention, quality of life, patient-reported global impression of change, and mood. We will assess feasibility with measurement of attendance at each class, and will assess preliminary sustainability with a six-month follow-up phone call to assess continued engagement in karate classes or other regular exercise. We will gather qualitative data on expectations and experience with the classes through pre-intervention and post-intervention focus groups.

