This is a non-randomized, open-label, non-blinded, 10-week pilot study of a novel intervention, namely, non-contact karate, for early to middle stage PD. The intervention—namely, karate classes—are developed for and will include only patients with Parkinson's disease. Eligible subjects will engage in twice-weekly karate classes for 10 weeks, specifically designed for individuals with early to middle stage PD, focused on incorporating upper and lower limb movements in multiple directions, increasing awareness throughout the body, shifting body weight and rotation, relaxation of the muscles, improving reaction time, using complex repetitive actions to improve coordination, footwork training and centered weight shifts to help with fall prevention, and striking shields for self-defense and stress relief.

Each subject will attend a pre-intervention focus group, at which time the study logistics will be reviewed, informed consent process will occur, the subject will complete a brief, individual pre-intervention assessment focused on overall mobility, gait, balance, attention, mood, and quality of life, and the subjects will be prompted to share aloud their thoughts on exercise, balance, and mindfulness practices in general and in PD specifically, and any expectations or preconceptions that they have regarding karate classes for PD. The focus group sessions will be audiotaped. After the sessions the information recorded will be transcribed into electronic documentation for later review and analysis. At the end of the study, the audiotapes will be destroyed.

Following 10 weeks of twice weekly classes, the subjects will have a post-intervention assessment and focus group, in which the pre-intervention assessments (TUG, FRT, TMT, PDQ-8, HADS, SDMT, DST) will be re-administered, along with the PGIC for the subject's global impression of change. Subjects will be prompted to share their thoughts on how the intervention impacted their overall wellbeing, balance, and mindfulness; whether the intervention achieved their expectations; and they will be asked to provide feedback for improvements. Finally, the study team will contact subjects 6 months post-intervention to assess continued engagement in karate or related activities and again, the subject's quality of life and global impression of change.

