3. Subjects unable to commit to attending, or to travel to, two classes weekly for 10 weeks.
4. Subjects previously participating in a karate or other martial arts program, including boxing programs for PD, in the past 30 days.

5. Subjects with atypical parkinsonism, including Progressive Supranuclear Palsy, Multiple System Atrophy, Dementia with Lewy Bodies, Corticobasal Syndrome, drug-induced parkinsonism, vascular parkinsonism, or atypical parkinsonism not otherwise specified, according to the referring neurologist.

II.g. Vulnerable Subjects – This study will not include children, prisoners, and homeless persons. The consent form will state that participation in our study will **not** affect their clinical care.

III. Methods and Procedures

Study Visits

Screening Phone Call

Subjects who are interested in participating based on review of printed or electronic recruitment materials will be directed to contact the study coordinator by phone, who will provide them with information about the study and the opportunity to ask questions about it in detail; those who express continued interest in participation will be screened for eligibility and ability to attend the scheduled classes, held at one of the five Fonseca Martial Arts Dojos in Glenview, Wilmette, Park Ridge, Evanston and/or Roscoe Village. Classes will occur twice weekly for ten weeks, between June through August 2018, and subjects can select from participating in either a weekend/weekday daytime class, or a weekday/weekday evening class, depending on their availability and proximity to each dojo's geographic location. Screening will occur on a rolling basis until the 15 slots in each class are filled.

Pre-Intervention Focus Group

Prior to the first class, subjects will attend a pre-intervention focus group, at which time the study team, including Principal Investigator, Research Coordinator, and research assistants, will review the study design and flow, informed consent process, and each subject will be individually visited by a member of the study team to review and sign the informed consent form (ICF).

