Subjects will then complete a brief demographic questionnaire, including duration of PD diagnosis in years, baseline activity level, prior involvement with karate or other martial arts, number of falls in the past 12 months, and subjects will complete the Parkinson's Disease Questionnaire-8 (PDQ-8)¹⁹, a brief, validated, PD-specific 8-item measure of quality of life. Subjects will complete the Hospital Anxiety and Depression Scale (HADS). Subjects will also write their response to the open-ended prompt, "What do you hope to achieve in this class?"

Subjects will then meet with a study team member to complete the TUG (see description below), FRT, and TMT. Next, the subject will meet with the PI or another study team member in a private room for a brief assessment of bradykinesia, tremor, rigidity, and postural stability in order to determine baseline HY stage. Lastly, subjects will meet with a study team member to complete short attention assessments with a SDMT and DST. Once all subjects have completed the pre-intervention written and physical assessments, the focus group will commence.

Subjects will be prompted to share aloud their thoughts on exercise, balance, and mindfulness practices in general and in PD specifically, and any expectations or preconceptions that they have regarding karate classes for PD.

Intervention

Each karate class will follow a structured curriculum, as shown in Appendix 1, with complexity of movements and movement patterns increasing over the 10-week study period. Classes will take place twice weekly, and subjects will be required to attend their assigned class time/location. Each class will last approximately 45-60 minutes. Attendance will be recorded in hard copy by the instructors at each class, with recordings only of the subject's name, not linked to their unique study ID; the attendance log will be shared with the study coordinator following the final class. A member of the study staff will be present at each class in order to answer questions and to support participants and instructors should any questions about protocol or PD safety arise.

Post-intervention focus group

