Six month follow-up phone call

The study team will contact the subjects by phone six months after the final class to ask whether the subject has continued to participate in any structured karate or martial arts classes; if yes, frequency and location will be asked. If no, reasons for lack of participation will be asked. Finally, PGIC will be administered a final time.

Assessments: Subjects who agree to be part of the study and sign the Informed Consent Form will be asked to complete a series of assessments to assess their current neurological status and overall wellbeing. There is no known risk associated with participation in these assessments, and they are a part of routine clinical care for these conditions. These tests are typically experienced as interesting to subjects. Administration of these assessments should take 15 minutes per subject immediately prior to the first class, and 15 minutes per subject immediately after the final class. All or some of the following assessments and self-report measures may be administered but are not limited to:

- *Demographic/disease questionnaire:* This brief, one-page questionnaire will ask for the subject's name, phone number (for 6-month follow-up call), age, gender, race, ethnicity, PD duration in years, prior exposure to karate or martial arts classes, baseline activity level, and number of falls in the past 12 months. There will be one open-ended question asking, "What do you hope to achieve in this class?"
- *Hoehn and Yahr Scale (HY):* A system used for describing how Parkinson's symptoms progress and the relative level of disability. There are five stages: Stage 0 – No signs of disease; Stage 1 – Unilateral disease; Stage 1.5 – Unilateral plus axial involvement; Stage 2 – Bilateral disease, without impairment of balance; Stage 2.5 – Mild bilateral disease with recovery on pull test; Stage 3 – Mild to moderate bilateral disease; some postural instability; physically independent; Stage 4 – Severe disability; still able to walk or stand unassisted; Stage 5 – Wheelchair bound or bedridden unless aided.²⁰

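### The six-month call and its analysis omit two items the protocol says it will assess: other regular exercise and quality of life

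*Combined protocol and SAP*

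**What the plan says.** Four places in the combined protocol and SAP describe the six-month contact.

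- **Opening statement of aims (before I.b).** The investigators "will assess preliminary sustainability with a six-month follow-up phone call to assess continued engagement in karate classes or other regular exercise".
- **I.c, Study Design.** The team will contact subjects "to assess continued engagement in karate or related activities and again" the subject's "quality of life and global impression of change".
- **III, Six month follow-up phone call.** Staff "ask whether the subject has continued to participate in any structured karate or martial arts classes". Those who say yes are asked how often and where. For the rest, "If no, reasons for lack of participation will be asked". The call ends with the PGIC.
- **III.b, Data Analysis.** The six-month analysis consists of descriptive statistics on continued karate or martial arts and the PGIC response percentages. The PDQ-8, the protocol's quality-of-life scale, is analysed only from before to after the intervention.

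**The concern.** The sections that state the purpose of the call are wider than the sections that say what will be asked and analysed. Call staff work from the procedure, so the procedure decides which data exist.

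Two things are at stake. First, the aims treat other regular exercise as part of preliminary sustainability. A subject who has left karate but exercises regularly would be recorded only as not continuing karate, and the data could not separate that person from someone who has stopped exercising. Second, six-month quality of life would not be measured at all.

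**Working it through.** No formula applies and the plan gives no figure to reproduce. The check sets each six-month item against the four places that could mention it.

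| Six-month item | Aims | I.c | Call procedure (III) | Analysis (III.b) |
|---|---|---|---|---|
| Karate / martial arts | yes | yes | yes | yes |
| Other regular exercise | yes | unclear (related activities) | no | no |
| Quality of life | no | yes | no | no |
| PGIC | no | yes | yes | yes |

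Items promised in the aims or I.c: 4. Items with both a question in the call and an analysis: 2. Items with neither: 4 − 2 = 2.

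I then looked for text that might close the gap.

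1. **The open-ended assessment list in III.** It allows for measures beyond those listed, but its stated timing is "15 minutes per subject immediately prior to the first class, and 15 minutes per subject immediately after the final class". It does not govern the call.
2. **The question on reasons for stopping karate.** A subject may mention other exercise in reply. That question goes only to those who did not continue, does not ask about exercise, and has no analysis in III.b.
3. **The PGIC as a stand-in for quality of life.** Section I.c names the two separately. The instrument descriptions define the PGIC as a single rating of overall response to the intervention and the PDQ-8 as the quality-of-life measure.
4. **Section V.d (Debriefing).** It mentions the call but adds nothing to its content.

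None of these supplies the missing items.

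One related wording point: the PGIC entry in the assessment list restricts the scale to the post-intervention assessment, whereas I.c, the call procedure and III.b all use it at six months too.

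**The case against.** The strongest reply is that each promise rests on one overview phrase. Other regular exercise at six months appears only in the aims, and six-month quality of life only in I.c. The call procedure and the analysis agree with each other, so the wider phrases may be loose summary wording rather than lost outcomes. Preliminary sustainability is not one of the two numbered aims, and everything planned at six months is descriptive.

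Much of this is fair. The documents do not show which version was intended, so narrowing the overview text is a legitimate repair. Recording a subject who left karate as not continuing is also correct for the question actually asked; the loss is a missing second item. The count of two in four describes the mismatch and does not measure its effect. The word 'only' in the PGIC entry may simply mean that the scale is not given at baseline, so that point adds little.

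The mismatch itself still stands. Section I.c is current protocol text stating what will be assessed at six months, yet it names no quality-of-life instrument for that time and the call script has no such step. Unless the sections are reconciled before the calls begin, the narrower version takes effect by default.

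**Conclusion.** The concern holds. Two of the four items promised at six months, other regular exercise and quality of life, have no question in the call and no analysis. The karate part of the sustainability question can be answered as written; the other-exercise part cannot, and six-month quality of life cannot be reported.

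The consequence is limited. None of the three hypotheses uses six-month data, and the sample size rests on the Timed Up & Go. No effect size can be given, because the documents contain no figures on exercise or quality of life at six months. It should be corrected because the loss would be permanent and the repair is small.

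The conclusion assumes that staff follow the call procedure as written and that the part of section V (recruitment and consent) not available to me contains no fuller call script.

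**What to change.** Choose one of two routes before the calls begin.

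**Route A: collect the items.**

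- *Call procedure (III):* add the PDQ-8, and one question to all subjects on the type and frequency of other regular exercise. Align its wording with the baseline activity item; the documents do not give that item's text.
- *Analysis (III.b):* summarise change in PDQ-8 from baseline to six months with a 95% confidence interval and the number of subjects with data, and note that administration moves from in person to telephone. Report the proportion in karate or martial arts and, separately, the proportion in karate or any other regular exercise, each set against baseline activity level.
- *Reason for the baseline comparison:* the only activity-related exclusion in II.f is "Subjects previously participating in a karate or other martial arts program, including boxing programs for PD, in the past 30 days", so subjects may enter already exercising in other ways. Exercise that predates the study should not be read as an effect of the programme. The baseline questionnaire already collects what is needed, "including duration of PD diagnosis in years, baseline activity level, prior involvement with karate or other martial arts".
- *Aims and I.c:* use one description of the activity in both.

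**Route B: narrow the promise.** Delete other regular exercise from the aims and quality of life from the six-month sentence in I.c, and replace the reference to related activities there with karate or martial arts.

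Under either route, amend the PGIC entry to name both the post-intervention assessment and the six-month call.

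**Cost.** Route A adds eight items and one question to a call already planned, probably a few minutes (my estimate), with no extra visit. Route B costs only wording but gives up both outcomes.

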The PI and research team will collaborate with a professor of Cinema and Television Arts from Columbia College Chicago, IL to develop a documentary to educate others about karate as an interactive form of exercise and its potential benefits on the symptoms and quality of life of people with PD. To capture the groups' journey over 10-weeks, portions of the pre-intervention focus group, the karate classes, and the post-intervention focus group will be videotaped. For a more in-depth look, two to three subjects will be followed during the entire study and interviewed to provide a personal narrative of their experiences with the karate classes and living with PD. The interviews will be videotaped.

We will recruit 30 individuals with PD diagnosed by a neurologist, ages 30-90, living in Chicago, and with Hoehn & Yahr (HY) stage 1 (unilateral symptoms, no balance issues), stage 2 (bilateral symptoms, no balance issues), or stage 3 (bilateral symptoms, some postural or balance involvement). Subjects will be assigned to one of two cohorts of 15 subjects each, based on dojo location and class schedule. For example, one cohort may take classes Tuesday and Thursday nights at the Wilmette dojo, and the second cohort may take classes Wednesday and Saturday mornings at the Glenview dojo, however class times and locations are to be determined.

II. Characteristics of the Research Population

II.a. Number of Subjects

Total Number of Subjects: 30

This is a pilot study; our power analysis (see table below) is based on the TUG, with the following assumptions: mean TUG score for individuals with PD is 14.8 seconds with standard deviation of 5.8 seconds, alpha of 0.05, and correlation between baseline and follow-up assessments of 0.5. We calculated sample sizes necessary with various minimum clinically important difference values for the TUG, which ranges from 2 seconds to 5 seconds in various studies^{1,18}, and varying for power between 80-90%. With a sample size of 30, we will have 80% power to detect a change of 3 seconds in the TUG, and will be more than 90% powered to detect a change of 4 seconds or greater.

| Baseline mean TUG | Baseline SD TUG | Min. clin. Important difference | Correlation b/w baseline, follow-up | Power | Sample size |
|-------------------|-----------------|---------------------------------|-------------------------------------|-----------|-------------|
| 14.8s | 5.8 | 2s | 0.5 | .9 | 89 |
| | | | 0.5 | .8 | 67 |

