In the week prior to the 10th class, the study team will contact subjects to remind them of the date and time of the final class and the post-intervention focus group. The post-intervention assessment will consist of a repeated TUG, FRT, TMT, HADS, PDQ-8, SDMT, DST, brief question about falls in the past 10 weeks, and PGIC. Each subject will receive their initial response to the "What do you hope to achieve in this class?" prompt, and will be asked to reflect in a written, open-ended manner on whether they feel that they achieved their goal. In addition, subjects will indicate their response to the following questions regarding feasibility: "Would you recommend this program to someone else with PD?" and "If available, would you continue to participate in this or a similar karate class?"

Subjects will then participate in a focus group, similar to the pre-intervention focus group, in which they be asked to share and reflect on how the intervention affected their overall attitude towards exercise; how it affected their balance and falls; how it affected their mindfulness; any other positive or negative benefits; any impact on their care partner(s) (if applicable); and suggestions for changes to the intervention for the future. Depending on availability of space, the post-intervention focus group may take place at Rush University, or may take place immediately following the last class at the respective dojo.

Documentary

Portions of the focus groups and karate classes, and the entire in-depth interview will be videotaped by the Columbia filmmakers using personal equipment. Subjects may choose to not participate in the documentary project which means subjects will not participate in the in-depth video interviews, and they will not be included in individual or group video shots during the focus groups and karate classes. To ensure confidentiality, subjects will be placed in one of two groups, Group A or Group B, depending on whether they decide to participate in the documentary or not. Subjects who agree to be videotaped and possibly interviewed will be part of Group A while subjects who choose not to be videotaped or interviewed will be in Group B. Subjects may not switch groups after the study begins with the pre-intervention focus group. Participation in the karate classes and focus groups will not be affected if a subject does not wish to be videotaped or interviewed. Subjects will not be penalized if they decide to not take part in the documentary

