- *Timed Up and Go (TUG):* A well-validated, brief measure of mobility. Administered by a study team member with a stopwatch who has previously measured out the distance between a standard arm chair and a taped line on the ground 10 feet (3 meters) away, subjects sit in a standard arm chair and are instructed that when the team member says "Go", they should stand up from the chair, walk at their normal pace to the line, turn, walk back to their chair at a normal pace, and sit down again. The study team member will record the TUG results in seconds using a stopwatch. This is a recommended test of balance in PD.²¹
- *Functional Reach Test (FRT):* This brief, valid, reliable, and practical assessment of balance involves a yardstick being mounted on a wall at shoulder height. The subject is asked to stand next to the yardstick, extend the arm closest to the wall at 90 degrees of shoulder flexion, and the distance is recorded. The subject is then asked to reach as far as he or she can forward without taking a step, and the distance is recorded again. The difference between start and end position is the reach distance.³ This is a recommended test of balance in PD.²¹
- *Tinetti Mobility Test (TMT):* This balance scale has strong psychometric properties and consists of 2 subscales: balance tests (9 items, scored from 0-16) and gait tests (7 items, scored from 0-12), where higher scores reflect better performance.⁵ This meets criteria for a "suggested" scale in PD. This is a recommended test of balance in PD.²¹
- *Hospital Anxiety and Depression Scale (HADS):* Brief, 14-item highly validated scale for measuring anxiety (7 items) and depression (7 items), where scores of >8 for either anxiety or depression indicate probable symptoms.⁶ The HADS was selected due to its use in prior peer mentoring studies and strong psychometric profile

- *Modified Unified Parkinson's Disease Rating Scale (UPDRS)*: A shortened version of the UPDRS motor subscale will be conducted by the PI or study staff, assessing only rigidity, resting tremor, and bradykinesia in all four extremities and the head/neck, as well as postural stability, in order to determine the subject's HY stage.

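### Repeat tests are timed straight after the final class while baseline precedes any class, so the uncontrolled pre-post change can include one class's acute effect

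*Combined protocol and SAP*

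**What the plan says.** **Baseline.** Section III, Pre-Intervention Focus Group: "Prior to the first class, subjects will attend a pre-intervention focus group". The questionnaires, TUG, FRT, TMT, staging examination, SDMT and DST are done in that session, and "Once all subjects have completed the pre-intervention written and physical assessments, the focus group will commence". Baseline therefore comes before any exposure to karate.

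**Class.** Section III, Intervention: "Each class will last approximately 45-60 minutes". The sample curriculum in Appendix 1 includes squats, kicks, strikes and stance work.

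**Repeat tests.** Section III, Assessments, is the only text that times them relative to the final class: "15 minutes per subject immediately prior to the first class, and 15 minutes per subject immediately after the final class". Section I.c says only that they follow the 10 weeks of classes. Section III, Post-intervention focus group, lists the battery without a time and then says "Subjects will then participate in a focus group, similar to the pre-intervention focus group", so testing comes before the discussion. It adds: "Depending on availability of space, the post-intervention focus group may take place at Rush University, or may take place immediately following the last class".

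**Cohorts.** Section I.c: "Subjects will be assigned to one of two cohorts of 15 subjects each, based on dojo location and class schedule".

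**Analysis.** Section III.b plans paired t-tests or Wilcoxon tests on the change in TUG, FRT, TMT, HADS, PDQ-8, SDMT and DST, stratified by Hoehn and Yahr stage. There is no control group.

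**The concern.** Followed as written, the plan compares subjects who have not exercised that day's class with subjects who have just finished one. Fatigue could hide a training gain in the timed and balance tests; warm-up could imitate one. With a single arm and a paired test, nothing in the analysis can separate one session's effect from that of ten weeks.

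Hypothesis 1 (change in TUG) and the exploratory gait, balance and attention outcomes are the ones at stake. The Rush University option adds a second problem. If one cohort were tested at the dojo after class and the other elsewhere at another time, the two would carry the acute effect to different degrees. No rest period, interval or matched test conditions are set for either venue.

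**Working it through.** **1. Timing, side by side**

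| | Before training | After training |
|---|---|---|
| Relative to a class | Before the first class | Immediately after the final class (Assessments), or unstated if at Rush University (Post-intervention focus group) |
| Order of tests | Questionnaires, then TUG, FRT, TMT, staging, SDMT, DST | Listed with TUG first; no order stated |
| Rest or interval rule | None needed | None given |

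**2. The plan's own sample size.** Inputs from section II.a: SD 5.8 s, correlation 0.5, alpha 0.05 (taken as two-sided), change 3 s, power 80%.

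- SD of change = 5.8 × √(2 × (1 − 0.5)) = 5.8 s.
- n = (5.8 × (1.960 + 0.842) / 3)² = 29.3, rounded up to 30.

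This matches the table, and the other seven entries also reproduce. This normal approximation gives 80.9% power at n = 30. The paired t-test gives 78.2%, and that value is used below.

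**3. What an acute shift would do (illustration).** The size of the shift is an assumption; the documents give none. Model: pooled paired t-test, n = 30, 29 degrees of freedom, two-sided 5%, counting rejections in the direction of improvement. The critical value is 2.045, so the smallest significant mean change is 2.045 × 5.8 / √30 = 2.17 s. The noncentrality is (net shift / 5.8) × √30.

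| Scenario | Net shift | Noncentrality | P(significant improvement) |
|---|---|---|---|
| No training effect, no acute effect | 0 s | 0 | 2.5% |
| No training effect, 0.5 s acute speeding | 0.5 s | 0.472 | 6.6% |
| No training effect, 1 s acute speeding | 1 s | 0.944 | 14.8% |
| True 3 s gain, no acute effect | 3 s | 2.833 | 78.2% |
| True 3 s gain, 0.5 s acute slowing | 2.5 s | 2.361 | 62.6% |
| True 3 s gain, 1 s acute slowing | 2 s | 1.889 | 44.7% |

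**4. If the effect fades.** Further assumptions: the effect halves every 30 minutes, and the 15 subjects of a cohort are tested in consecutive 15-minute slots by 2 to 4 testers. The average remaining share is then 42% to 66%. A 0.5 s effect at class end gives 3.9-4.9% false improvement and 72-68% power. A further wait of 15 to 30 minutes before the first test gives 3.1-4.0% and 75-71%.

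**The case against.** **Post-class testing is not certain.** A reader might infer that every subject will be tested just after exercise. The documents do not support that. The Assessments sentence mainly describes test burden, and the Rush University option leaves another time open. What stands is that this sentence is the only timing relative to the final class, so staff following the plan would test then, and nothing fixes the alternative.

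**The size is assumed.** This is correct. No passage shows that a class alters a TUG in which subjects are told "they should stand up from the chair, walk at their normal pace to the line". The shift, its fading, the number of testers and the test order are all supplied here. If questionnaires came first, as at baseline, subjects would sit before being timed and the effect would be smaller. A reader might also infer from the table that the bias favours karate; its sign is unknown.

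**The figures are for a pooled test.** Section III.b stratifies by stage. In a stratum of, say, 10 subjects (assumed), a 1 s shift gives 7.1% rather than 14.8%, and power for 3 s is only 31% before any acute effect. The illustration does not carry over to analyses within stage.

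**Self-reports.** HADS and PDQ-8 sit in the same battery and paired analysis, and PGIC is also collected at this session. Mood straight after a group class might colour all three. The documents do not show that it does, nor that any of them is immune.

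**A single-arm pilot is confounded anyway.** True, and it limits how much this matters. Practice and expectation cannot be removed without a comparator, but this component can be removed by scheduling.

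**Conclusion.** The concern holds as a correctable weakness in scheduling, worth considering rather than serious. The stated timing lets the paired change in TUG, FRT, TMT, SDMT and DST include one class's acute effect, and the Rush University option leaves the interval unfixed and possibly different between cohorts.

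The magnitude is hypothetical. It rests on an assumed shift common to all subjects, a pooled t-test on 30 and the plan's SD and correlation. On those terms even 0.5 s would matter for Hypothesis 1 in either direction, and less so if it fades before testing.

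Two further readings are not supported. The sample-size calculation is not at fault: it reproduces. And correcting the timing would not make a TUG change attributable to karate, because practice and expectation effects remain in a single-arm design.

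**What to change.** Reconcile the Assessments and Post-intervention focus group texts with one rule for both cohorts:

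- Do TUG, FRT, TMT, SDMT and DST, and preferably HADS and PDQ-8, before the final class starts, in the baseline order and under conditions matching baseline.
- Record the time since the last class for each subject.
- Leave PGIC, the recommend and continue questions, and the focus group after the class.

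**Cost.** The outcome is measured after 19 of 20 classes. Subjects arrive earlier in staggered slots, and testing space is needed before class, which no section assures. The testing load does not grow: 15 subjects × 15 minutes = 225 minutes, or 3.75 tester-hours per cohort. That is 75 minutes with 3 testers or 45 with 5. Some subjects would have a longer day.

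**Alternative.** A separate non-class day avoids the early arrival but adds a trip, and section V.f provides no compensation. If 3 of 30 post-tests were lost (an assumption), power for 3 s would fall from 78% to 73%.
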